The MetS was found to be an independent risk factor for falls in a study of 1165 community-dwelling older adults (8). Similar studies of community-dwelling older adults have found that falls are associated with abdominal obesity, which is the core diagnostic criterion of the MetS (9, 10). Obesity has been shown to positively correlate with impaired postural balance, even in individuals under 40 years of age (44). More importantly, obesity, which was defined as a BMI greater than 30 kg/m^2 , was found to be associated with a higher prevalence of falls in middle-aged and older adults (11). This definition of obesity ($> 30 \text{ kg/m}^2$) is the same used by the International Diabetes Federation in definition of the MetS that states that central obesity can be assumed and waist circumference does not need to be measured (45).

Reducing risk of falls

Weekly balance training sessions have been shown to reduced fall risk in patients with diabetic peripheral neuropathy (46, 47). In a group of patients with moderate diabetes and minimal neuropathy it was found that a 12 week training program resulted in increased gait velocity, balance, muscle strength and joint mobility, and decreased fear of falling (46). The “feet first” trial prospectively observed falls after a home based strength and balance program in individuals with diabetic peripheral neuropathy. This study did not show a reduction in fall occurrence but falls were not the primary outcome, the majority of exercises were performed at home without supervision and less than half (45%) of the participants in the intervention group reported compliance with more than half of the study protocol (48). Evidence for the importance of a group or observed training program come from a study of home based vs. center based balance and strength training for community dwelling adults. This study by Comans et al. showed that the center based exercise program yielded significantly better results in terms of falls prevention (49)

However, to our knowledge there have not been any prospective randomized intervention trials to determine if the risk of falls can be reduced in patients with the MetS. Knowledge gained from this pilot project will determine how the chosen outcome measures perform as part of an intervention study in this patient population and provide information to properly power a future clinical trial.

Possible Mechanisms Underlying Expected Reduction in Fall Risk

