Sample Size Calculation

The FSST was chosen as the primary efficacy measure because it has been demonstrated to be a reliable and valid clinical test of fall risk. Importantly, it has been shown to have a higher sensitivity and specificity than the Timed Up and Go test, the Step Test and the Functional Reach Test for identifying differences between groups of older adults; non-fallers, non-multiple fallers, and multiple fallers (14). In normal controls the FSST has been shown to have a standard deviation of 2.34 seconds (74). A minimal detectable change has not been established in a population of elderly adults who are at risk for falls. However, in other populations of patients with neurological disorders that had a similar age and mean score at baseline the minimal detectable change estimate for the FSST was 4.6 seconds (75).

Table 3. Number of Subjects Required for a Range of Mean Differences in FSST

Smallest detectable mean difference in FSST (SD=2.34)	Number of subjects per group	Actual Power
1.0	87	0.800
1.5	40	0.808
2.0	23	0.809
3.0	11	0.816
4.0	7	0.835

Sample size per group required for to detect a specified mean difference in FSST at 12 weeks based on a two sample t test, power=0.8, significance level=0.05

Based on the FSST, the required sample size to detect a difference of 2.0 seconds is 23 participants per group. Based on results from similar intervention studies, the drop-out rate is up to 25% (14, 76). Allowing for a 10% drop-out rate in the standard care group, we will need to recruit 26 participants into the standard care group and 29 participants into the balance exercise group for a total of 55 participants.

Statistical Analyses

The two treatment groups will be compared using baseline demographic variables (age and gender) and relevant prognostic covariants (history of falls, BMI, abdominal circumference, fasting glucose, BP, lipids, SAS score, and baseline values of primary endpoints). These variables will be tested for baseline comparability using a univariate analysis. The variables will also be examined by stratified analysis to

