determine if any of them are potential effect modifiers or confounders. [The unadjusted associations between covariates and the primary outcome variable will first be examined. The covariates that are found to have statistically significant associations with both the exposure and the outcome variables will be examined by stratified analysis to determine if they are potential confounders. All covariates will be examined by stratified analysis to determine if they are potential effect modifiers. If there are potential effect modifiers, interaction terms will be included in the logistic regression model. If the interaction terms are found to be significant in the model, indicating that there is effect modification, then the final analysis will be stratified].

An intention to treat analysis will be used. Descriptive statistics will be used to assess the distribution of the FSST. Bivariate analysis including Chi-square and t-tests to compare the categorical and continuous variables will be performed. Mean and standard deviation for the FSST at each time point will be computed and analysis of variance will be used to compare the means of the two treatment groups, controlling for baseline characteristics. The main hypothesis is that the participants in the balance exercise program will show a greater improvement in the FSST at 12 weeks compared to baseline than the participants in the standard care group.

Table 4. Hypothesis Testing Plan

Endpoints	Baseline	12 weeks
Primary	FSST	FSST
Secondary	Instrumented DGI (time spent in double support)	Instrumented DGI (time spent in double support)
Tertiary	ABC scale	ABC scale
Exploratory 1	ActiveStep (recovery steps)	ActiveStep (recovery steps)
Exploratory 3	Autonomic testing	

[Primary hypothesis] – the change in FSST from baseline to 12 weeks will be compared between the standard care and exercise intervention groups to determine if there is a significantly significant difference between the two groups. (covariates included in the model will include outcome at baseline, gender, age, race, and intervention group)

Secondary hypothesis – the change in the DGI score and time spent in double support on the instrumented DGI from baseline to 12 weeks will be compared between the standard care and exercise intervention groups to determine if there is a statistically significant difference between the two groups.

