[All participants will attend weekly sessions at the Baltimore VA annex. Participants in the intervention program will attend weekly group training sessions and those in the control group will attend weekly group health education classes. In order to avoid drop-out from the study, all participants will also keep an exercise log of home activity and they will be contacted by phone if they do not attend a weekly group session.

Furthermore participants will be reimbursed for parking for each weekly visit and an additional \$25 for the screening, enrollment, and the 12 and 24 week visits. This is important because many Veterans in Baltimore have limited income and the cost of travel and parking is a potential limitation to subject participation.

Upon completion of the initial 12 week intervention period the participants who had been randomized to the control group will be offered the exercise intervention for an additional 12 weeks (enrolled in the study for a total of 24 weeks). Due to concern regarding an unknown washout period those participants initially randomized to the intervention program cannot serve as their own controls but they will be followed without further intervention and reassessed at 4 week intervals (weeks 16, 20, 24) to gain additional information about what the length of the washout period might be.]

Balance exercise program

Subjects in the balance exercise program will participate in a three month exercise program designed to improve balance. Balance exercises will be performed three times per week in a home-based training program and participants will also attend a weekly group training session at which time participants will be instructed on the proper performance of the exercises and how to progress the exercises if appropriate. If a participant is unable to attend one of the weekly group sessions they will be contacted by phone and will continue the exercises performed in the previous week.

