Progression of the balance exercise program will depend on the individual participant's ability to complete 3 sets of 10 repetitions of a particular exercise using smooth, controlled movements. At the weekly group session the trainer will determine if a participant should progress a particular exercise and will instruct the participant on how to progress. The participant will continue these exercises as instructed at home for the next week. Once a participant can complete 3 sets of a given exercise they will be given personalized instructions to progress the exercise. All participants will initially perform the exercises with hold support that will be progressed by instructing them to gradually reduce their reliance on external support. Once they can demonstrate that they can safely perform 3 sets of the exercise with minimal support the exercise will be progressed to be performed without support (**Table 6**). For the side and forward/backward stepping the participants will be instructed to take narrower steps and to vary the pace of the steps or to perform the exercise with their eyes closed. The side stepping exercises can also be made more challenging by using cross-over steps forward and backward in addition to direct lateral side steps. The alternating toe touches will be advanced by increasing the speed of the movements, varying the width of the base of support, and by instructing the participants to simultaneously move their arms by lifting light hand weights. The walking exercises will be progressed by varying step length, width, and speeds, stepping over objects, and using different lighting intensities.

Table 6: Balance Training Program Progression:

Exercise	Level A	Level B	Level C	Level D	Level E	Level F
Side stepping	10 steps Hold support	10 steps No support	10 steps Vary step length	10 steps Vary step speed	10 steps Eyes closed	
Forward/Backward stepping	10 steps Hold support	10 steps No support	10 steps Vary step length	10 steps Vary step speed	10 steps Cross-over steps	
Alternating toe touch to box	5 touches per side Hold support	5 touches per side No support	5 touches per side Increase speed	5 touches per side Vary width of base of support	5 touches per side Simultaneously move arms	5 touches per side Add hand weights
Tandem walking	10 steps Hold support	10 steps No support	10 steps Vary step speed	10 steps Vary light intensity		

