The SC group will be assigned an interventionist assessor for the duration of the study. This assessor will meet with the subjects during their orientation meeting and will be provided information about falls and recommendations for fall prevention. There will be no directed program throughout the study. [Participants in the standard care group will also meet in person on a weekly basis for general education class regarding health and fall prevention but will not participate in an exercise class. They will also be asked to keep a log of any exercise that they perform at home. This will attempt to control for the effects of coming into a facility once a week in both the standard care and balance exercise intervention.]

At the completion of the study participants in the standard care group will receive instruction in the balance exercise program so that they may benefit from the program as well.

Intervention Timeline

Initially enrollment will be slow to pilot the intervention program and will aim to enroll one or two participants. The next two waves of patients will include 4 to 6 participants and afterwards each wave will include approximately 8 participants. This will require approximately 48 months to complete the intervention for 55 participants.

Table 7: Intervention Program Timeline:

Group (n)	Months																	
	1-3	4-6	7-9	10-12	13-15	16-18	10-21	22-24	25-27	28-30	31-33	34-36	37-39	40-42	43-45	46-48	49-51	52-54
1 (1 - 2)	x	x																
2 (4 - 6)			x	x														
3 (4 - 6)					x	x												
4 (8)							x	x										
5 (8)									x	x								
6 (8)											x	x						
7 (8)													x	x				
8 (8)														x	x			
Recruitment	x	x	x	x	x	x	x	x	x	x	x	x	x	x	x	x		
Screening	x	x	x	x	x	x	x	x	x	x	x	x	x	x	x	x	x	
Enrollment	x	x	x	x	x	x	x	x	x	x	x	x	x	x	x	x	x	
Outcome Assessment			x	x	x	x	x	x	x	x	x	x	x	x	x	x	x	x

Data management

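### Both arms are treated in small weekly groups, but the sample size and the FSST model allow for no correlation within a group; if that correlation is material, the planned test's error rate rises above 5%

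*Combined protocol and SAP*

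**What the plan says.** **Delivery.** Under Intervention Programs, "Participants in the intervention program will attend weekly group training sessions and those in the control group will attend weekly group health education classes". Under Balance exercise program, the group session also steers the home exercises: "At the weekly group session the trainer will determine if a participant should progress a particular exercise", and those instructions apply at home for the following week.

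**Wave size.** Intervention Timeline and Table 7 describe a first wave of 1 to 2 people, two waves of 4 to 6, and "afterwards each wave will include approximately 8 participants", eight waves in all. Randomization Scheme gives equal allocation in blocks of 2 to 4 within fall-history strata.

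**Sample size.** Table 3 is headed "Sample size per group required for to detect a specified mean difference in FSST at 12 weeks based on a two sample t test". It gives 23 per group and power 0.809 for a 2.0 s difference with SD 2.34 s. No ICC or design effect is mentioned.

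**Analysis.** Statistical Analyses says "analysis of variance will be used to compare the means of the two treatment groups, controlling for baseline characteristics". The primary model lists baseline FSST, gender, age, race and arm, and the analysis is also stratified by fall history. No wave, trainer or session-group term appears for any endpoint.

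**The concern.** People who attend the same weekly group share sessions and peers, and in the exercise arm they share the trainer's progression decisions. If this makes their 12-week FSST results more alike than those of people in other groups of the same arm, the independence assumption fails. The standard error of the difference is then too small, the interval too narrow, and the test rejects too often when there is no effect.

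The trial is a pilot, but it still runs a formal significance test on the FSST. One of its declared purposes is to "provide information to properly power a future clinical trial", so it matters whether its standard error is sound. If session group is not recorded, clustering may be impossible to examine afterwards.

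**Working it through.** **Inputs from the documents.** Difference 2.0 s, SD 2.34 s, 23 evaluable per arm, α 0.05 (Sample Size Calculation, Table 3); eight waves (Table 7); 1:1 blocked allocation (Randomization Scheme). Sidedness is not stated.

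**Assumptions, not in the documents.** ICC from 0 to 0.20. Eight groups per arm with evaluable sizes 1,3,3,3,3,3,3,4 (set A) or 1,2,2,3,3,4,4,4 (set B); both sum to 23. Total SD is held at 2.34 s.

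**1. The plan's own figure.** Noncentrality = 2.0 / (2.34 × √(2/23)) = 2.0 / 0.690 = 2.898, with 44 df and two-sided critical value 2.015. Power is 0.809, and 22 per group gives 0.791. The stated 23 and 0.809 reproduce under independence. (A one-sided test would give 0.887, so two-sided is the evident intent.)

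**2. Effective group size.** m = Σs²/Σs. Set A: (1 + 6×9 + 16)/23 = 71/23 = 3.09. Set B: (1 + 4 + 4 + 9 + 9 + 16 + 16 + 16)/23 = 75/23 = 3.26.

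**3. Planned test, clustering in both arms.** Design effect DE = 1 + (m − 1) × ICC. The type I error of the unclustered test is approximately P(|t₄₄| > 2.015/√DE). For set A at ICC 0.05, DE = 1 + 2.09 × 0.05 = 1.104 and the error is 6.2%. Simulation with both sets of sizes (60,000 to 200,000 trials per scenario) agrees:

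| ICC | DE, set A / set B | Type I error, formula | Type I error, simulated | Rejection rate at 2.0 s, simulated |
|---|---|---|---|---|
| 0 | 1.00 / 1.00 | 5.0% | about 5% | 0.81 |
| 0.01 | 1.02 / 1.02 | 5.2% | 5.1–5.2% | 0.81 |
| 0.05 | 1.10 / 1.11 | 6.2–6.3% | 6.1–6.5% | 0.80 |
| 0.10 | 1.21 / 1.23 | 7.4–7.6% | 7.4–7.7% | 0.79 |
| 0.20 | 1.42 / 1.45 | 9.8–10.2% | 10.0–10.7% | 0.77 |

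For set A the true standard error exceeds the assumed one by √1.104 = 1.05 at ICC 0.05 and √1.209 = 1.10 at ICC 0.10. The interval is too narrow by about those factors.

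**4. Other correlation patterns.**
- Exercise arm only: type I error is about 5.5% at ICC 0.05 and 6.2% to 6.4% at ICC 0.10.
- A wave effect shared equally by both arms: about 4.5% at ICC 0.05 and 4.0% at ICC 0.10. The effect cancels in the comparison and the test becomes slightly conservative.

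**5. A group-level analysis, no baseline adjustment.** With 8 + 8 − 2 = 14 df and noncentrality 2.898/√DE (set A):

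| ICC | Noncentrality | Power at 2.0 s |
|---|---|---|
| 0 | 2.898 | 0.77 |
| 0.05 | 2.758 | 0.73 |
| 0.10 | 2.636 | 0.69 |
| 0.20 | 2.435 | 0.62 |

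Set B gives values within 0.01. The fall from 0.809 to 0.77 at ICC 0 comes entirely from having 14 rather than 44 df.

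**The case against.** The strongest reply is that nothing in the documents establishes a material ICC.

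- Most of the exercise is done at home, three times a week against one group session, and progression is tailored to the individual.
- The text refers to a trainer without saying that trainers differ between waves. One trainer throughout would not create differences between groups.
- Controls attend education without exercise, so a group effect on a timed stepping test is doubtful in that arm.
- Calendar effects are common to both arms of a wave.

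All of this stands, and it is why the error rate can only be stated conditionally. It does not remove the pathway, because the group session sets the next week's home exercises. Clustering in the exercise arm alone still raises the error rate, though by less.

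A reader might also infer that the groups are closed and number four per arm. The documents do not say so. Table 7 shows enrolment in nearly every period and waves 7 and 8 overlapping, four per arm fits only the later waves, and a first wave of 1 or 2 people may not fill both arms.

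A reader might further infer that the power is really 0.73 rather than 0.809. That is not supported either. The 0.73 belongs to an unadjusted 14-df test that the plan does not propose. The planned model adjusts for baseline FSST, which Table 3 ignores. The documents give no baseline-to-12-week correlation. If it is assumed to be 0.5, power at ICC 0.05 (DE 1.10) is about 0.84 on 13 df; if 0.3, about 0.76.

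Finally, the pilot will estimate the ICC poorly. At a true ICC of 0.05, simulated estimates span −0.26 to 0.37 (95% range) and 41% are zero or negative. That limits its value for planning the next trial, but does not affect the case for protecting this trial's error rate.

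**Conclusion.** The point holds conditionally. Both arms are delivered in small groups, and neither the sample size nor any endpoint model allows for correlation within them. At an assumed group-specific ICC of 0.05 to 0.10, the planned FSST test has a type I error of about 6% to 8%, or about 5.5% to 6.4% if only the exercise arm clusters, and its interval is about 5% to 10% too narrow.

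It would go too far to say that the stated power and 5% error rate are not delivered. At ICC 0 to 0.01 they essentially are, and at ICC 0.05 to 0.10 the planned test's rejection rate at 2.0 s is still 0.79 to 0.80. The fault is in error control; the power cost appears only once the analysis respects the groups. These figures rest on an assumed ICC, inferred group sizes and an unadjusted test.

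**What to change.** 1. **Data collection:** record each participant's session group (wave × arm) prospectively.
2. **Statistical Analyses:** for the FSST, prespecify a model with the covariates already listed plus a random intercept for session group, with Kenward-Roger degrees of freedom. At minimum, make it a sensitivity analysis reported beside the planned model. Do the same for the DGI, ABC and ActiveStep endpoints.
3. **Reporting:** give the ICC with its confidence interval, and say that about 16 very small groups make it imprecise.
4. **Sample Size Calculation:** keep 0.809, but state that it assumes independence and an unadjusted t test. Add that an unadjusted group-level analysis with 23 per arm would have power of about 0.77, 0.73, 0.69 and 0.62 at assumed ICCs of 0, 0.05, 0.10 and 0.20, before any gain from baseline adjustment.

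The cost is one recorded variable, a few sentences and a somewhat wider interval. Blinding and Unblinding Plan has the statistician finalise the analysis plan at study completion, so the model wording can still be changed. The session-group variable cannot wait, because it has to be captured as sessions run.

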The database manager utilizes a structured data entry system into a database with range checks on individual items and double keying to ensure accuracy. Data are entered into computers as per standard protocols. Data are cleaned and edited after being transported into a statistical software package. Protocols have been developed to handle missing or out of range values, documentation, file backup and archiving, and confidentiality procedures. The VA statistician, [name], will participate in the design of the protocols, choice of software platforms, computer data organization and structures, merging data sets, and data transport.

Blinding and Unblinding Plan

Only the research assistant and the biostatistician, neither of whom will be responsible for assessment of the outcome measures, will handle the randomization list with subjects' names. The treatment allocation list will be blinded to the investigators who measure the outcome measures. The main study data will be kept in a separate database with only the dummy ID. Unblinding prior to the completion of the study will be granted only for urgent clinical reasons, such as a subject has an urgent medical problem or has developed a serious adverse event, which requires the intervention allocation be made available. Otherwise, unblinding will occur on completion of all the recruitment and study measures. Unblinding is achieved by merging the main database with the treatment allocation list. At completion of the study, the study database will be locked. The statistician will finalize the statistical analysis plan and perform the analysis on the locked database.

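### Nothing requires the SAP to be final before outcomes are joined to allocation, and the primary FSST model is still partly open at that point

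*Combined protocol and SAP*

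**What the plan says.** The Blinding and Unblinding Plan gives this sequence:

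- During the trial: "The main study data will be kept in a separate database with only the dummy ID".
- Apart from urgent clinical cases: "Otherwise, unblinding will occur on completion of all the recruitment and study measures".
- The mechanism: "Unblinding is achieved by merging the main database with the treatment allocation list".
- Then: "At completion of the study, the study database will be locked".
- Last: "The statistician will finalize the statistical analysis plan and perform the analysis on the locked database".

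No other section says when the SAP is to be final.

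Statistical Analyses already fixes much of the plan: FSST as primary endpoint, change from baseline to 12 weeks, and intention to treat. For the primary hypothesis it states that "covariates included in the model will include outcome at baseline, gender, age, race, and intervention group". It also says that "analysis of variance will be used to compare the means of the two treatment groups, controlling for baseline characteristics", and that the analysis will account for the fall-history stratum used in randomization. The monitoring plan rules out interim efficacy analyses.

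The same section leaves other choices to the data. Of the baseline variables it says "These variables will be tested for baseline comparability using a univariate analysis", with no threshold given. The adjusted analysis is then to include covariates found to differ between the groups, as well as the stratification factor. Interaction terms go into a logistic regression model, and a significant interaction makes the final analysis a stratified one.

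**The concern.** A SAP protects against choosing the analysis by its result only if it is final before anyone can see outcomes by arm. Here the text places finalisation alongside the analysis itself, after the merge and the lock.

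Timing and model specification are linked. Which covariates differ between the arms can be known only once baseline data carry arm codes, and the plan describes one merge, of the main study data. Followed as written, the covariate set is settled when FSST results by arm are also visible.

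The existing safeguards do not cover this. Blinded assessors and dummy IDs protect measurement and the period before the merge. The ban on interim efficacy analyses does not govern the choice of final model. The trial could show that its endpoint was pre-specified, but not that its primary model was. That matters somewhat even in a pilot, since the stated purpose is to plan and power a larger study.

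**Working it through.** **Step 1. Timing.** The plan states no figure on this point, so the check is a reading of the whole document. Unblinding is tied to completion of recruitment and measures, and lock to completion of the study. Neither is tied to a final SAP, and finalisation is mentioned once, after both.

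**Step 2. Does Statistical Analyses yield one primary model?** Set side by side, it does not:

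| Element | Reading 1 | Reading 2 |
|---|---|---|
| Covariates | Baseline FSST, gender, age, race, plus fall-history stratum | The same, plus any covariate that differs between arms |
| Model type | Analysis of variance on FSST means | Logistic regression, although FSST is a time in seconds |
| Final form | One overall comparison | Stratified if an interaction is significant |

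**Step 3. How often would the two covariate rules diverge?** Beyond the core set and fall history, the baseline comparison lists six headings: BMI, abdominal circumference, fasting glucose, BP, lipids and SAS score. So p = 6 further covariates; p = 7 if BP is split into systolic and diastolic; p = 10 if lipids are also split into four. With independent covariates, the chance of at least one imbalance at 0.05 is 1 − 0.95^p:

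- p = 6: 1 − 0.95^6 = 26.5%
- p = 7: 1 − 0.95^7 = 30.2%
- p = 10: 1 − 0.95^10 = 40.1%

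The simulation below gives 26-27%, 30-31% and 40%.

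**Step 4. Effect on false positives.**

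- Inputs from the plan (Sample Size Calculation): SD 2.34 s; 23 per arm, also run as 26 and 29. Table 3's power of 0.809 for 23 per arm and a 2.0 s difference reproduces with a two-sided two-sample t test at 0.05.
- Assumptions: no true effect; correlation between baseline and 12-week FSST r = 0.5, 0.65 or 0.8; age, fall history and each further covariate correlated 0 or 0.2 with FSST; 25% fallers, balanced by stratification; covariates independent of one another.
- Model A: 12-week change = arm + baseline FSST + gender + age + race + fall stratum.
- Model B: A plus every further covariate with between-arm p < 0.05.
- Open threshold: A, or B with the cut at 0.05, 0.10 or 0.20. The documents do not state the cut; these values are assumed.
- 20,000 trials per scenario, eight scenarios for each p; Monte Carlo standard error about 0.15-0.18 percentage points.

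False-positive rate (%), two-sided p < 0.05, range over the eight scenarios:

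| p | A alone | B alone | Better of A and B | Best of four (open threshold) |
|---|---|---|---|---|
| 6 | 4.88-5.21 | 4.69-5.13 | 5.38-5.68 | 6.28-6.45 |
| 7 | 4.85-5.13 | 4.67-5.06 | 5.37-5.62 | 6.28-6.61 |
| 10 | 4.74-4.90 | 4.49-4.88 | 5.42-5.62 | 6.55-6.88 |

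A and B disagree on significance in 0.9-1.2% of trials (p = 6), 1.0-1.3% (p = 7) and 1.3-1.7% (p = 10).

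Either rule alone holds its level; the inflation comes from being free to choose. The logistic and stratified branches are not in these figures. Real covariates such as BMI and waist are likely correlated, so the chance of some imbalance is probably overstated.

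**The case against.** **The order is inferred.** The text never says that the merge precedes the lock, and the reference to the locked database most naturally attaches to performing the analysis. Nor does it forbid comparing baseline data by arm before outcomes are joined. All of this stands, and it is why the claim is limited to a missing requirement.

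**The real defect is the model wording, not the date.** Signing the present text earlier would leave the data-driven covariate choice in place. That is correct, and the remedy therefore has to cover both.

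**The plan can be read as giving one model.** The primary hypothesis lists its covariates, the stratum is added, and the logistic wording may be a slip. But the text does not say whether the imbalance-driven expansion belongs to the primary analysis.

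**The size is overstated.** Statistical Analyses also describes a two-way screen, under which potential confounders must be significantly associated with both exposure and outcome. If that screen governs the expansion, the model departs from the fixed one in only 1.6-12.7% of trials, and taking the better of the two gives roughly nominal error, about 4.8-5.3%. The documents do not say that it governs, so the higher figures remain possible. It is also true that no passage permits running both rules and claiming the better; the point is that nothing would show which was chosen in advance.

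**The statistician already has allocation.** The study statistician issues the assignments and the biostatistician handles the randomization list, so finalising before the merge does not by itself guarantee a blinded author. Naming one fixed model deals with this, because it removes the choice whoever knows the allocation.

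**Conclusion.** The point holds and is minor. No section requires the SAP to be final before outcomes are joined to allocation or before lock, and the covariate set and form of the primary FSST model are unreconciled. Under the written covariate rules, and on the assumptions listed above, false positives rise from about 5% to 5.4-5.7%, or to 6.3-6.9% if the imbalance threshold is also open. They stay near nominal if the two-way screen applies. Ambiguity about which model is primary would be common (about 26-40% of trials on the imbalance rule at 0.05), but would seldom change the conclusion on significance (0.9-1.7%). The case for acting rests less on these figures than on being able to show that the model was chosen in advance, at almost no cost.

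**What to change.** Amend the Blinding and Unblinding Plan so that a dated, signed SAP is final before database lock and before outcomes are merged with the allocation list. In Statistical Analyses:

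- Name one primary model: a linear model for 12-week change in FSST with arm, baseline FSST, gender, age, race and the fall-history stratum.
- Make adjustment for covariates found imbalanced, and any stratified analysis, labelled sensitivity analyses.
- Correct the logistic regression wording for the FSST.
- Label any later change post hoc.

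The cost is about one paragraph of text and the same work done earlier. The drawbacks are less freedom to adapt the plan at the end, and that a covariate imbalanced by chance is handled only in a sensitivity analysis. Sample size, staffing, DSMB safety review and urgent unblinding are unaffected.
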